6.3 Subject withdrawal

6.3.1 Withdrawal

Subjects may withdraw from the study at any time for any reason, according to the terms of the Informed Consent document, which includes continuation of clinical study follow-up whenever possible, and ongoing medical care as appropriate. Subjects may also be withdrawn from the study at any time at the discretion of the investigator.

It should be understood that an excessive rate of withdrawals could render the study difficult to interpret. Hence, unnecessary withdrawal of subjects should be avoided. Should a subject withdraw or is withdrawn, every effort must be made to complete and report the observations as thoroughly as possible. If possible, in case of withdrawal, permission for yearly study telephone follow up to assess long-term outcomes and safety will be obtained from the subject.

6.3.2 Procedures for handling withdrawal

Subjects who withdraw or are withdrawn from the study should:

- Have the reason(s) for their withdrawal recorded (if possible).
- May be seen by an investigator and all final assessments should be performed and recorded.
- Be asked about the presence of any AEs. If an ongoing AE is present, the patient should be followed up until satisfactory clinical resolution of the event is achieved.

If a subject is withdrawn, Valtech monitor should be informed as soon as possible by the site. One additional subject will be enrolled for each subject withdrawn (or died) for any reason before the primary endpoint period completed.

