6. STATISTICAL ANALYSIS & DATA MANAGEMENT

6.1 Number of patients (sample-size)

Based on the results of the Cardioband CE mark study (Protocol ID CB 1-2), the present study with a sample size of 50 subjects will have greater than 80% power to detect a reduction in MR severity of at least one grade (CE mark study showed improvement in MR severity of at least one grade in >80% of subjects in CE mark study).

Based on the results of the Cardioband CE mark study (Protocol ID CB 1-2), the present study with a sample size of 50 subjects will have greater than 90% power to detect an improvement of 75 m in 6 minute walk test at 6 months

The PMS population may be expanded to collect additional experience from market introduction. This will also allow avoiding the potential influence of patients lost to follow-up or withdrawn.

	REPAIR - Transcatheter REPAIR of Mitral Insufficiency with Cardioband System Post Market Study Protocol ID CB1-3	
---	---	---

[figure not shown]

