6.2 Statistical rationale

6.2.1 Population: All patients Per Protocol

Endpoint: MR Reduction at 30 days

Estimates:

- Power: 80%, 90%
- Change in MR at 30 Days: 81.48%
- Two-tailed Alpha = 0.05
- Test: Exact Test
- Drop-out rate = 5%

[figure not shown]

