6.2.2 Population: All patients Per Protocol

Endpoint: Mean 6MW at 6 Months

Estimates:

- Power: 80%, 90%
- Mean 6Mw at 6 months: 50, 75 meters
- Standard Deviation = 139
- Treatment arms = 1
- Two-tailed Alpha = 0.05
- Test: One-sample t-test
- Drop-out rate = 10%

	REPAIR - Transcatheter REPAIR of Mitral Insufficiency with Carotiband System Post Market Study Protocol ID CB1-3	
---	---	---

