6.3.3 Lost to follow up

If a subject does not appear for a follow-up visit and cannot be contacted for collecting follow-up information the primary physician will be contacted and will be asked about the subject's health condition. At least 3 attempts should be made to contact the subject through all available routes attempt to contact the patient should be recorded. If there is no contact with the patients and/or primary physician - he/she will be considered 'lost to follow up'. One additional subject will be enrolled for each lost to follow up before the primary endpoint period completed.

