6.3.4 Referral for alternative treatments

Subjects may be referred, at the discretion of the investigator, for an additional structural heart treatment. In such cases, the subject will be followed according to the follow up plan to assess long-term safety. The follow up may be performed by telephone, to collect safety information

	REPAIR - Transcatheter REPAIR of Mitral Insufficiency with CaRdioband System Post Market Study Protocol ID CB1-3	
---	---	---

(occurrence of adverse events), and if possible information regarding clinical status, and changes in medications. One additional subject will be enrolled for each patient if treated before completing the primary endpoint period.

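### Early deaths, withdrawals, losses and re-treatments each trigger an extra enrolment, but no readable rule keeps those subjects in the efficacy analyses or says how they count, so a completer-type result is permitted

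*Combined protocol and SAP*

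**What the plan says.** Three rules add a subject when one is lost early. On withdrawal or death, section 6.3.2 says: "One additional subject will be enrolled for each subject withdrawn (or died) for any reason before the primary endpoint period completed". Section 6.3.3 says: "One additional subject will be enrolled for each lost to follow up before the primary endpoint period completed". On further structural heart treatment, section 6.3.4 says: "One additional subject will be enrolled for each patient if treated before completing the primary endpoint period".

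Section 6.1 allows the population to be expanded and gives as one reason: "This will also allow avoiding the potential influence of patients lost to follow-up or withdrawn". The sample-size inputs for the two powered endpoints, MR reduction at 30 days and 6MWT at 6 months, stand under the headings "6.2.1 Population: All patients Per Protocol" and "6.2.2 Population: All patients Per Protocol". No definition of that population is readable.

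Other text points towards keeping data. Section 6.3.1 asks that, after withdrawal, "every effort must be made to complete and report the observations as thoroughly as possible", and section 6.3.2 asks for final assessments. Section 6.3.4 keeps re-treated subjects on the follow-up plan, but adds: "The follow up may be performed by telephone, to collect safety information". Section 3.1 gives 50 subjects as a minimum.

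The period that governs the three triggers is not fixed. The synopsis and sections 3.2.1 and 6.2.1 place the primary endpoint at 30 days; section 3.1 places it at 6 months.

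**The concern.** If a subject who dies or is re-treated is followed by an extra enrolment, and the efficacy analysis then uses a per-protocol set, the result describes those who stayed in the study without further treatment. A single-arm trial has no control group in which the same selection would occur. Leaving out deaths and re-treated subjects is expected to favour the device; for other losses the direction is uncertain.

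The open window adds to this. On the 6-month reading, a subject with a measured 30-day MR result who dies in month 4 triggers an extra enrolment. On the 30-day reading, losses between day 30 and month 6 trigger none, and no readable rule says how they enter the 6MWT analysis. If these choices are made after outcomes are known, the choice itself can bias the result.

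**Working it through.** **Inputs from the plan.** N = 50 (synopsis, 6.1). MR: response 81.48%, exact test, two-sided alpha 0.05, drop-out 5% (6.2.1). 6MWT: 75 m, SD 139 m, one-sample t-test, two-sided alpha 0.05, drop-out 10% (6.2.2). The synopsis also quotes an SD of 90.3 m from the CE mark study.

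**Assumed, because no figure is readable.** The MR comparator p0 (50 to 70%, defined on all treated subjects), that 81.48% is a rate among evaluable subjects, the response of lost subjects, and the baseline walk distance.

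**The plan's own powers.** 6MWT, noncentral t, 75 m, SD 139: 96.2% with 50 subjects and 94.3% with 45 (50 × 0.90), so the stated figure of more than 90% reproduces. For MR, the stated figure of more than 80% cannot be confirmed without a comparator. The table shows the range.

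**MR rate with losses kept in.** With share lost q and relative response f of lost subjects, rate = 0.8148 × [(1 − q) + q × f]. At q = 0.05:
- f = 0: 0.8148 × 0.95 = 77.4%
- f = 0.5: 0.8148 × 0.975 = 79.4%
- f = 1: 81.48%

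In whole subjects, 41/50 = 82.0% (exact 95% CI 68.6 to 91.4) becomes 41/53 = 77.4% (63.8 to 87.7) when three failures are kept in.

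**MR error and power, exact binomial, N = 50, upper tail at most 0.025.** The fourth column is the rejection rate of an evaluable-only analysis when the true all-treated rate equals p0 and the 5% lost all fail (evaluable rate p0/0.95). The last column is power at 77.4%, with the losses kept as failures.

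| p0 | Critical count | Error, no loss | Error, losses left out | Power, no loss | Power, 5% lost all fail |
|---|---|---|---|---|---|
| 50% | 33 | 1.6% | 3.9% | 99.7% | 97.8% |
| 55% | 35 | 2.2% | 5.4% | 98.4% | 91.9% |
| 60% | 38 | 1.3% | 3.8% | 87.9% | 66.7% |
| 65% | 40 | 1.6% | 5.0% | 68.5% | 40.5% |
| 70% | 42 | 1.8% | 6.2% | 40.5% | 17.3% |

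If losses respond at half the rate (evaluable rate p0/0.975), the error with losses left out is 2.3 to 3.5%, and power at p0 = 60% with them kept in is 78.6%.

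**6MWT with losses kept in.** Let a share q be scored as a change of −B: B = 0 for zero change, B = baseline distance for a death scored as 0 m. Then mean m = 75(1 − q) − qB and variance = (1 − q)(SD² + 75²) + qB² − m². The mixture is treated as normal. Example: q = 0.10, B = 0, SD 139 gives m = 67.5 and variance 0.9 × (19,321 + 5,625) − 4,556.25 = 17,895, so SD 133.8 and power 93.8%.

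| Scoring, N = 50 | Power, SD 139 | Power, SD 90.3 |
|---|---|---|
| 10% zero change | 93.8% | above 99% |
| 10% deaths at 0 m, baseline 100/200/300 m | 80/56/32% | 98/79/45% |
| 4% deaths at 0 m, baseline 100/200/300 m | 92/86/77% | 99.9/99.0/95.1% |

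**The case against.** A reader might infer that early losses are replaced, meaning taken out and substituted. The documents do not support that. The word used is additional, no passage removes anyone, and a top-up fits a target stated as a minimum. The label on the population is a sample-size heading and could simply mean all patients under the protocol. The section 6.1 sentence concerns an optional expansion and can be read as protecting numbers. Section 6.3.4 puts re-treated subjects on the follow-up plan, which includes echo and walk test; telephone contact is only permitted. Figures in sections 6.1 and 6.2 are not shown and might hold a definition. All of this stands, and it limits the point to what the plan permits.

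It does not close the gap. Requests to complete observations govern data collection, not analysis, and nothing further can be observed in a subject who has died. Appendix 2 lists procedural mortality and unplanned device-related procedures under device failure, but nothing links that list to either powered endpoint.

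A reader might also infer that early deaths disappear from the trial's results. They do not: all-cause mortality with major adverse events, and days alive and out of hospital, are secondary endpoints (3.2.3), and serious events go to the events committee (7.2). Only the efficacy analyses are affected.

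The sizes depend on assumptions. If the comparator is itself a rate among evaluable subjects, or losses respond like the rest, there is no inflation. At comparators of 65 and 70% the MR power is below 80% before any loss, so that shortfall is not caused by this gap.

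**Conclusion.** The concern holds as a missing analysis rule together with a contradictory trigger window. The plan permits a completer-type result for MR and 6MWT; it does not require one. The bias is expected to favour the device where deaths and re-treatments are left out.

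At the plan's 5% drop-out the effect on the MR rate lies between none and about 4 percentage points (81.48% to 77.4%), given the assumption that 81.48% is an evaluable-subject rate. For 6MWT, the scoring rule can decide whether more than 90% power is kept: it holds with zero change for 10% of subjects at either SD. With 10% deaths scored as 0 m it fails at every assumed baseline with SD 139, and at 200 and 300 m with SD 90.3. The conflict between 30 days and 6 months is wrong as written and needs correcting whatever is decided on the rest.

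**What to change.** 1. Make all subjects with an attempted implant the primary efficacy set. For MR, count death or mitral re-intervention before the 30-day visit as non-response. State how a missing echo is handled and add a sensitivity analysis that counts it as non-response. Define per protocol and keep it as a sensitivity analysis.
2. State in 6.3.2 to 6.3.4 that every subject with an attempted implant who triggers an extra enrolment stays in that set. Report subjects lost before an implant attempt separately. Delete the 6.1 sentence on avoiding the influence of losses.
3. Prespecify one rule for death and inability to walk in the 6MWT analysis, with one sensitivity analysis under a different rule.
4. Reconcile sections 3.1 and 3.2.1 on the primary endpoint time, and define the primary endpoint period from it.

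**Cost.** The edits are wording. The result may look slightly less favourable, and both powers must be restated for the chosen comparator, SD and rules. More subjects may be needed. At an assumed 60% comparator with 5% lost, 53 subjects (50 plus three extra, all kept) give 70.0% power if all losses fail and 81.4% at half response. Reaching 80% takes about 60 to 63 subjects in the first case and 48 to 51 in the second; exact power moves in steps, hence the ranges. Sections 3.1 and 6.1 already allow more than 50.

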6.3.3 Lost to follow up

If a subject does not appear for a follow-up visit and cannot be contacted for collecting follow-up information the primary physician will be contacted and will be asked about the subject's health condition. At least 3 attempts should be made to contact the subject through all available routes attempt to contact the patient should be recorded. If there is no contact with the patients and/or primary physician - he/she will be considered 'lost to follow up'. One additional subject will be enrolled for each lost to follow up before the primary endpoint period completed.

6.3.4 Referral for alternative treatments

Subjects may be referred, at the discretion of the investigator, for an additional structural heart treatment. In such cases, the subject will be followed according to the follow up plan to assess long-term safety. The follow up may be performed by telephone, to collect safety information

	REPAIR - Transcatheter REPAIR of Mitral Insufficiency with CaRdioband System Post Market Study Protocol ID CB1-3	
---	---	---

(occurrence of adverse events), and if possible information regarding clinical status, and changes in medications. One additional subject will be enrolled for each patient if treated before completing the primary endpoint period.

6.4 Information collected in the Case Report Forms (CRFs)

The study physician or his designee at each clinical site will perform primary data collection. The CRFs will be collected in an electronic version. Only the study physician or other pre-designated study personnel will be authorized to enter data (from source documents).

Only anonymous data will be collected after the patient has consented that personal data can be used.

6.5 Source Documents

Source documents are original hospital records, clinical charts, screening log, patient identification list/enrolment log, original laboratory report, recorded data from automated instruments, imaging data, subject's files, and records kept at the laboratories and medico-technical departments involved in the study. The investigator must maintain source documents for each patient in the study. All information recorded on the eCRFs must be traceable to these source documents.

6.6 Site Documentation

Each clinical site will maintain a Regulatory Binder that includes all the required document (per ISO 14155:2011 - Clinical investigation of medical devices for human subjects), the laws and regulations of the countries where the PMS will take place, and indemnity / insurance requirements.

6.7 Data Retention

All study records and reports must remain on file for at least the number of years required by the local regulations after the completion or termination of the study. Study records are to be discarded only upon notification by Valtech. If audits are required, the Principal Investigator shall allow access to the original medical records and provide all requested information.

The study physicians should contact Valtech before the destruction of any records and reports pertaining to the study to ensure they no longer need to be retained. In addition, Valtech should be notified if the study physician plans to leave the institution.

6.8 Study Monitoring

Valtech or its designees will conduct investigational site monitoring to ensure that all investigators are in compliance with the investigational plan and the Investigator's Agreement. The monitors will verify source documentation against completed eCRF's according to a risk based monitoring approach.

	REPAIR - Transcatheter REPAIR of Mitral Insufficiency with Cardioband System Post Market Study Protocol ID CB1-3	
--	---	--

Each site will be visited regularly, according to the monitoring plan, to ensure that the study is conducted in full compliance with all applicable regulations and the investigational plan.

6.9 Investigational Site Initiation and Training Requirements

Prior to investigation site activation, Valtech will provide study training relevant and pertinent to the involvement of personnel conducting study activities, investigator responsibilities, as well as device training.

6.10 Study Closeout

Upon completion of the study (when all subjects enrolled have been followed at 2 years and the eCRFs and queries have been completed), a close-out visit will be performed. All unused study materials and equipment will be collected and returned to Valtech or designee. The Monitor will ensure that the study physician's regulatory files are up to date and complete and that any outstanding issues from previous visits have been resolved. Other issues which will be reviewed at this visit include: discussing retention of study files, possibility of site audits, publication policy, and to ensure that the study physician will notify the local ethics committee and/or competent authority regarding study closure, if needed.

7 SAFETY EVALUATION AND REPORTING

7.1 Adverse event definitions

For purposes of this protocol cardiac adverse event definitions are provided in Appendix 2; Definitions of Adverse Events according to *The Mitral Valve Academic Research Consortium*

	REPAIR - Transcatheter REPAIR of Mitral Insufficiency with CaRdioband System Post Market Study Protocol ID CB1-3	
--	---	--

(MVARC) Guidelines: Clinical Trial Design Principles and Endpoint Definitions for Transcatheter Mitral Valve Repair and Replacement (JACC 2015;66(3):278-307). Reporting procedures

Appendix 1 of this protocol provides detailed information on investigator responsibilities for assessing and reporting adverse events. All adverse events will be reported and recorded throughout the clinical investigation; each event will be followed until adequately resolved or explained. A list of expected AEs, which may result from the study procedure, is included as part of the IFU.

The Principal Investigator must determine whether the adverse event meet the definition of "serious" (Appendix 1). The investigator(s) will report any serious adverse event to the Valtech's Clinical Research department without unjustified delay.

Valtech or its designee will determine reportability of applicable adverse events according to its responsibilities for vigilance reporting.

7.2 Clinical Events Committee

All Serious adverse events will be reviewed by an independent Clinical event Committee (CEC) for adjudication of the event relation to the study device or procedure. 

7.3 Subject deaths

In the event of subject death, every effort should be made to obtain a copy of the autopsy report and/or death summary. Information on the cause of death and its relationship to the device used in this clinical investigation will be determined by the principal investigator. Copies of an autopsy report, if available, and/or a death summary are to be sent to the Investigation Sponsor.

If a device is explanted during autopsy, the device should be returned to the Sponsor for investigation and analysis. Return kits for devices will be provided upon request by the clinical monitor.

7.4 Termination criteria

The sponsor may suspend or prematurely terminate either a clinical investigation in an individual investigation site or the entire clinical investigation for significant and documented reasons. If suspicion that the disadvantages of participation may be significantly greater than those foreseen, the sponsor shall suspend the Study while the risk is assessed. The Principal Investigator shall promptly inform the enrolled subjects at his/her investigation site, if appropriate.

	REPAIR - TranscatheteR REPair of MitrAl Insufficiency with CaRdioband System Post Market Study Protocol ID CB1-3	
---	---	---

8 STUDY CONDUCT AND RESPONSIBILITIES

8.1 Regulatory compliance

This study will be conducted in conformity with the ethical principles set forth by the Declaration of Helsinki, Good Clinical Practice (GCP) principles, international harmonized standards for clinical investigation of medical devices (ISO 14155:2011, Clinical investigation of medical devices for human subjects), the laws and regulations of the countries where the study will take place, and indemnity / insurance requirements.

8.2 Informed consent procedure

Patient authorization and written informed consent must be obtained prior to the patient's enrolment into the Study and in accordance with GCPs, the Medical Devices Directive and all other applicable standards, regulations (local and national), guidelines and institutional policies.

The patient will also give his written consent for health information release, i.e. screening informed consent, in order to determine if the patient is a potential candidate for the device.

8.3 Confidentiality

Patient confidentiality must be maintained in accordance with GCPs, the Medical Devices Directive and all other applicable standards, regulations (local and national), guidelines and institutional policies. Study physicians will comply with the applicable provisions of the study agreement with regard to nondisclosure and confidentiality.

8.4 Device Accountability

The Investigator shall document in the procedure reports and eCRFs the serial/lot number of all devices used during procedures.

8.5 Protocol Changes/Amendments

The investigators will not deviate from the protocol except in emergency circumstances to protect the rights, safety and well-being of the patients. Deviations shall be documented and reported to the sponsor and the EC, if applicable, as soon as possible. Valtech or its designee will evaluate circumstances where an investigator deviates from the investigational plan.

Amendments to the protocol or any study documents already approved by the EC must be submitted and approved before the changes are implemented. For non-substantial changes [e.g.

	REPAIR - Transcatheter REPair of Mitral Insufficiency with CaRdioband System Post Market Study Protocol ID CB1-3	
---	---	---

minor logistical or administrative changes, change of monitor(s), telephone numbers, renewal of insurance], a simple notification to the EC and, where appropriate, regulatory authorities may be sufficient.

	REPAIR - TranscatheteR REPair of MitrAl Insufficiency with CaRdioband System Post Market Study Protocol ID CB1-3	
---	---	---

9 Appendices

